- ***Treatment can be initiated with an on-demand regimen. Prophylaxis should begin after a minimal number of on-demand FVIII exposures with BAY 81-8973 (no more than 2-3 bleeding events) or when the child is large enough to tolerate weekly infusion. (as of Amd 1 and 6)***
- ***Alternatively, prophylaxis can be started directly with a once-a-week schedule low dose of 250 IU (15-25 IU/kg); the starting dose may be tailored to the subject's weight or demonstrated bleeding tendency. (as of Amd 1 and 6)***
- ***Increase frequency of infusion or dose as needed for breakthrough bleeding, increased physical activity, or weight gain. (as of Amd 1)***
- ***Avoid starting prophylaxis during febrile illness or other identified inflammatory events. (as of Amd 1)***
- ***Avoid surgery or need for high dose intensive treatment lasting more than 4 days during the first 20 ED. (as of Amd 1)***
- ***Do not give FVIII as prophylaxis for vaccinations. (as of Amd 1)***

After treatment with BAY 81-8973 begins (as of Amd 1), inhibitor testing every 3-5 ED is required (as of Amd 1) until 20 ED are accumulated or in case of non-response to treatment (Section 14.5) (as of Amd 1)

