Hemophilia A is a genetic bleeding disorders caused by the deficiency of Factor VIII (FVIII). Persons with mild hemophilia (6% – 49% Factor level) may have excessive bleeding following dental procedures, injury or surgery, while moderate (1% to 5% factor activity) and severe (< 1% factor activity) hemophilia are typically characterized by more frequent and severe bleeding complications. Persons with severe hemophilia may experience not only bleeding after injury, trauma or surgery, but also spontaneous bleeding into joints, muscles and internal organs, including the brain. Recurrent bleeding into joints results in chronic debilitation.

The standard treatment for hemophilia A is replacement therapy, with intravenous (IV) administration of plasma-derived or recombinant FVIII. Some subjects treat bleeding episodes as they occur (i.e., on-demand [OD] treatment), while others treat themselves prophylactically to prevent bleeding according to the recommendations from the World Health Organization. In recent years, prophylactic treatment has become the prevailing type of hemophilia treatment in most developed countries.

The proven clinical benefits of prophylaxis have led to a shift in treatment paradigm from OD treatment to the use of prophylaxis in many countries.

Effective treatment options are significantly lower if inhibitory antibodies against the FVIII (inhibitors) develop. The inhibitors interfere with the infused factor concentrates rendering them ineffective and requiring the use of high dosed FVIII (Imune Tolerance Induction [ITI]) or costly and less effective alternative hemostatic agents, defined as "bypassing agents". The incidence of new FVIII inhibitors in subjects with severe FVIII deficiency is up to half of the patients. Inhibitor development is currently the most significant treatment complication seen in subjects with hemophilia. While improvements in hemostatic agents for subjects with significant morbidity, including a higher rate of bleeding complications, increased disability, and a decreased quality of life.

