4.5.2 Annualized bleed rate

The definition of annualized bleed rate is generally defined as

```
(#of bleeds in period) * 365.25/(last datetime of period- first datetime in period)
```

```
60 \cdot 60 \cdot 24
```

The different periods used for analysis are described in section 6.2.1.

4.5.3 24 hours rule

Count no more than 1 bleed in a calendar day. If there is more than 1 bleed in a calendar day, to determine the bleed that gets counted, give priority to treated bleeds, spontaneous or trauma bleeds, then joint bleeds. Otherwise, count the first bleed in the day. Severity and treatment response will come from this selected bleed. Bleed site will be aggregated over all bleeds from that day. Regardless of which bleed is selected, the time of the first bleed in the day will be used. All other infusions in the day for treating bleeds will be considered follow-up infusions.

4.5.4 72 hours rule

Do not count a spontaneous joint/muscle bleed if it occurs within 72 hours of a bleed (or infusion for that bleed) at the same site. For a bleed to be affected by this rule, all sites listed on the bleed must also be specified in the previous bleed. If the current and previous bleeds are both skin/mucosa bleeds, this rule does not apply. Such infusions for bleeds will be considered to be follow-up infusions.

Joint bleeds can occur in more than 1 joint site. For each joint bleed, count all sites (combining left and right). For the table showing the Joint Site frequency, sum counts over all sites.

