5.1 Assignment of analysis sets

Final decisions regarding the assignment of subjects to analysis sets will be made during the review of study data and documented in the final list of important deviations, validity findings and assignment to analysis set(s) (see section 4.6).

The statistical analysis sets are defined as follows:

SAFety analysis set (SAF)

All subjects with at least one intake of study drug.

Subjects who were assigned to treatment but did not receive study medication will not be included in the SAF. As the number of these excluded subjects is anticipated to be negligible, if at all any exist in this design, an "all assigned treatment analysis set" will not be generated.

(modified) Intent To Treat Set (ITT)

All subjects of the SAF, who have infusion/bleeding data.

Per Protocol Set (PPS)

All ITT subjects who completed Part A and Part B of the study with no major protocol deviations.

Major protocol violations would be for example:

- Severe hemophilia A not confirmed
- Evidence of inhibitor antibody present at the time of screening.
- MTP has previously received more than 3 exposure days with any FVIII product, PUP has received any amount of FVIII
- In the prophylactic period here was/were at least
 - \circ one instance of >30 days between infusions
 - \circ two instances of >21 days between infusions
 - \circ three instances of >14 days between infusions

PharmacoKinetic Analysis Set (PK)

Statistical Analysis Plan PH-41074 Protocol No.: BAY 81-8973 / 13400

Page: 12 of 19:

Not applicable to this interim analysis, as it is not expected to get enough subjects for a reasonable analysis from part B. There will be an analysis of the pharmacokinetic data for the final CSR.

Listing Only Set (LOS)

Subjects who do not belong to SAF will not be included into statistical considerations. These subjects are classified as 'listing only set' (LOS). Number of screening failures and dropouts will be tabulated.

6. Statistical Methodology

The efficacy analyses will be based on the ITT and sensitivity analyses will be based on the PPS as appropriate.

The primary analysis population for the safety analysis will be the SAF.

6.1 **Population characteristics**

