6.2 Efficacy

All subjects receiving study drug who have infusion/bleeding data from the EPD will be included in the efficacy analysis.

Primary Efficacy Analysis

The primary efficacy variable according to protocol will be the annualized number of total bleeds (sum of spontaneous bleeds, trauma bleeds, untreated bleeds, and 'other' bleeds) that occur within 48 hours after all prophylaxis infusions. 'Other' bleeds are infusions with reason given as 'other'.

For this primary efficacy variable, the number of data available and missing data, mean, standard deviation (SD), minimum (Min), quartiles, median, and maximum (Max) will be summarized and presented.

Additional Efficacy Analysis

Also summarized will be annualized number of joint bleeds, spontaneous bleeds, and trauma bleeds that occur within 48 hours after all prophylaxis infusions. Additional variables summarized will be annualized number of total bleeds, joint bleeds, spontaneous bleeds, and trauma bleeds as well as the annualized numbers.

Other variables summarized will be the number of treatments required to control all bleeds and the subject's assessment of the response to treatment of all bleeds (excellent, good, moderate, or poor), further on description of joint bleeds according to site as well as proportion of subjects with no bleed

FVIII usage/consumption will be described expressed as number of infusions, number of prophylaxis infusions, and number of infusions to treat breakthrough bleeds. Infusions will be summarized in IU, IU/kg, IU/kg/year, IU/kg/infusion, IU/year, and IU/infusion.

All efficacy variables will be summarized using the ITT analysis set. The summary of bleeds, the exposure to study drug and the treatment administration for bleeds will also be given in the ITT.

The number of infusions used to treat a bleed will be summarized. The number of infusions used to treat a bleed is defined as the first infusion to treat the bleed plus all follow-up infusions to treat the same bleed, if any. The proportion of bleeds controlled by ≤ 2 and ≥ 2 infusions will be presented.

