6.2.2 Subgroup analysis

Subgroups of analysis are already described in 4.1:

- ➤ type of subjects: PUPs; MTPs; total
- inhibitor status: Subjects without inhibitor; Subjects with low titer inhibitor; Subjects without inhibitor or with low titer inhibitor; Subjects with high titer inhibitor
- > inhibitor status of PUPs: The same as above restricted to PUPs

These different periods for analysis are planned:

Period	Definition	To be used
Total part B period	MAINSDTM to MAINEDTM	always
		for response to
On-demand period	if OD_STDTM >. : OD_STDTM (is equal to	treatment of
	MAINSDTM) to OD_EDTM	bleeds

Statistical Analysis Plan PH-41074

Protocol No.: BAY	81-8973 / 13400
-------------------	-----------------

Page: 15 of 19:

Period	Definition	To be used
Prophy period (without once per week treatment)	if an infusion with EXSCATN = 8 exists and last infusion with EXSCATN = 8 < MAINEDTM: last infusion with EXSCATN = 8 to MAINEDTM. If last infusion with EXSCATN = 8 is at MAINEDTM no such period exists. If no infusion with EXSCATN = 8 exists: PX SDTM to PX ENDTM.	later for publications
Prophy period (including once per week treatment)	if SDTM > .: PX SDTM to PX ENDTM	always
Total treatment period (starting after 1st treatment)	TRTSDT to MAINEDTM	always
Period of once per week treatment only	if an infusion with EXSCATN = 8 exists: if OD_STDTM ne . then PX_SDTM to last infusion with EXSCATN = 8 else TRTSDT to last infusion with EXSCATN = 8	later for publications
Period of high inhibitor of high titer inhibitor subjects	if HINHSDTM < HINHEDTM: HINHSDTM to HINHEDTM	For extension only
Period of total inhibitor of high titer inhibitor subjects	if HINHSDTM > .: INHSDTM to INHEDTM	For extension only
Period of total inhibitor of low titer inhibitor subjects	if HINHSDTM = . and INHSDTM < INHEDTM: INHSDTM to INHEDTM	ABR & response to treatment

Further specification of the different periods are as following:

- The **total part B period** starts with the baseline visit and ends with the final visit. In case the study drug were already administered between the screening visit and the baseline visit, the period starts with the date of injection.
- The **on-demand period** starts with the first injection in an on-demand schedule and ends with the start of the prophylaxis period or final visit, whatever comes first.
- The **prophylaxis** period starts with the first and ends with the last injection of prophya ctic study drug.

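### The Part B primary bleed rate is not tied to one analysis period, so a child who never received prophylaxis scores either 0 or nothing, depending on the period used

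*SAP*

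**What the plan says.** **Variable.** Part B SAP v2.0, section 6.2, counts total bleeds "within 48 hours after all prophylaxis infusions" and annualizes them. It names no period. It asks for the numbers of available and missing values but does not say which children are missing.

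**Population.** Section 6.2 states: "All subjects receiving study drug who have infusion/bleeding data from the EPD will be included in the efficacy analysis". Section 5.1 defines the ITT as "All subjects of the SAF, who have infusion/bleeding data". Neither asks for a prophylaxis infusion.

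**Route into the analysis without prophylaxis.** Protocol 6.1.1 says of Part B: "Treatment can be initiated with an on-demand regimen". Prophylaxis follows after at most 2-3 bleeds or once the child is big enough. SAP 6.2.2 says the on-demand period "ends with the start of the prophylaxis period or final visit, whatever comes first", so it can run to the end of Part B.

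**Formula and periods.** Section 4.5.2 multiplies the bleeds in a period by 365.25 and divides by its length in days. Section 6.2.2 marks three periods for use *always*: total Part B, total treatment, and prophylaxis including once-weekly treatment. Only the last depends on a prophylaxis start date.

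**Protocol wording.** Protocol 7.3.1 describes the primary variable as bleeds during prophylaxis, within 48 h of the last prophylaxis infusion.

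**The concern.** A bleed can enter the 48 h count only if a prophylaxis infusion came before it. A child treated only on demand has no such infusion, so his count is zero by construction, not because prophylaxis worked. If that zero is divided by a positive length of time, he is recorded as a perfect result on a variable to which he contributes no information. Such a child may have bled repeatedly, or left because of an inhibitor. Each such zero pulls down the mean, and can pull down the median and quartiles, of the main efficacy result.

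**Working it through.** The plan states no figure for this point. Section 9.1 of the Part B SAP says there was no formal sample size determination. The check applies the SAP's own rules to a child with no prophylaxis infusion.

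**Step 1: is he in the analysis?** Yes, if he received study drug and has infusion or bleeding data (5.1, 6.2).

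**Step 2: his primary value under each *always* period.** Let T be the period length in days.

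| Period (6.2.2) | Exists for him? | Rate (4.5.2) |
|---|---|---|
| Total Part B | Yes, baseline to final visit | 0 × 365.25 / T = 0 |
| Total treatment | Yes, first study drug to final visit | 0 × 365.25 / T = 0 |
| Prophylaxis, including once weekly | No, there is no start date | No value |

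The zero holds for every T > 0 and is the minimum of the variable.

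**Step 3: his actual bleeding.** The same formula on all bleeds gives, over 60 days, 1 × 365.25 / 60 = 6.1, 2 × 365.25 / 60 = 12.2 and 3 × 365.25 / 60 = 18.3 per year. Over 30 days, 1, 2 or 3 bleeds give 12.2, 24.4 or 36.5. The counts and durations are illustrative.

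**Step 4: effect on the mean.** If the other N-k children have mean m, adding k zeros gives m(N-k)/N. Protocol 8.6 plans at least 25 children plus about 25 more in Part B; k is assumed.

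- N = 50: k = 1 gives 49/50 = 0.98 (2% lower); k = 3 gives 47/50 = 0.94 (6% lower).
- N = 25: k = 1 gives 24/25 = 0.96 (4% lower); k = 3 gives 22/25 = 0.88 (12% lower).
- Section 4.1 also shows efficacy by inhibitor status. In a column of n children one zero lowers the mean by 1/n; with n = 5, assumed for illustration, that is 20%.

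**Step 5: does another rule settle it?**

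- Part B SAP 4.2 calculates annualized total bleeds for withdrawn children. It does not mention the 48 h variable.
- Part B SAP 4.3 has no rule for a child without prophylaxis.
- Supplement 1.0, section 2.1, ties the secondary total bleed rate to prophylaxis treatment but adds nothing on the primary variable.
- The Part A SAP, section 4.5, starts the clock at the first prophylaxis dose and ignores earlier bleeds, but it covers previously treated patients only.

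**The case against.** The best defence is that *no value* is the more natural reading. Section 6.2 presents the variable as the protocol's, the protocol ties it to prophylaxis, and 6.2.2 has a matching period that exists only once prophylaxis has started. A child without it would then fall into the missing count that 6.2 already requires. This reading is sensible, and the fix adopts it. But 6.2 does not state it, and two other *always* periods produce a zero from the same formula.

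The SAP introduction also places data-handling detail in separate TLF specifications and Analysis Datasets documents. These were not available and may settle the point. Even so, the choice between 0 and missing for the primary variable belongs in the SAP text.

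The harm is also limited. Results are shown by inhibitor status, so a child lost to an inhibitor cannot lower the column without inhibitors. Reasons for leaving are tabulated and individual values listed. The analysis is descriptive. The end bound of the on-demand period may be routine drafting, since Part B children must agree to start prophylaxis (protocol 5.1.1). These points limit the size of the problem but do not remove the zeros from the total columns.

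A reader might go further and infer how many children are affected from the SAP introduction, where inhibitor incidence is put at up to half. Spreading that risk evenly over 20 exposure days, with 2-6 on-demand days first, gives 1 - 0.5^(2/20) = 6.7% to 1 - 0.5^(6/20) = 18.8%; at a 30% risk, 3.5% to 10.1%. The documents do not support using these as estimates:

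- The half is a background ceiling with no 20-day window.
- The even spread and the length of the lead-in are assumptions.
- Developing an inhibitor is not the same as leaving. The first scheduled test is at 4 ± 1 exposure days and a positive result needs confirmation, so prophylaxis could begin first.
- Protocol 7.3.2.2 records an infusion after trauma without bleeding as prophylaxis, so some on-demand children would not be forced to zero.

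**Conclusion.** The point holds as a gap in the definition of the primary variable. Applied as written, the SAP gives a child without prophylaxis the best possible score in two of the three standard displays and no score in the third. The zero is a consequence of the formula; no SAP rule awards it. A reader might conclude that early inhibitor loss is bound to improve the efficacy result. The documents do not show that: the prophylaxis-period display is unaffected if he is left without a value there, and the number of such children is unknown.

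The size depends wholly on that number. With 1 to 3 such children the overall mean falls by 2-6% at N = 50 or 4-12% at N = 25, and by more in a small inhibitor-status column. This should be corrected in the SAP, but it does not undermine a descriptive analysis. The conclusion assumes that the unavailable data-handling documents do not already contain the rule.

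**What to change.** Add to Part B SAP 6.2 that the primary variable is calculated over the prophylaxis period, including once-weekly treatment, for ITT children with at least one prophylaxis infusion. Children with none are set to missing, not 0, in every display of the 48 h variable, whichever period it uses. Beside the primary table, report how many there are, why they did not start, and their all-bleed rate.

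The same text should cover a child with exactly one prophylaxis infusion. Section 6.2.2 runs the prophylaxis period from the first to the last prophylactic injection, which leaves this child a period of zero length.

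The cost is a short addition to the SAP, one extra table row, and a primary denominator slightly below the full ITT. Treatment and data collection do not change.

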7.1.2 Timing of assessments

The main study consists of a Screening period *followed by at least 50 ED* per subject. *The Screening and Baseline visits may be combined to one visit for PUPs. There is no minimum interval between the Screening and Baseline visits for PUPs/MTPs (as of Amd 6) or PTPs. For PTPs, no longer than 8 weeks should pass between Screening and Baseline visits. (as of Amd 1)*

In Part A, PTPs, a minimum of 50 ED will be accumulated during a 6 month treatment period. Visits are scheduled at Month 1, Month 2 and Month 6. (as of Amd 1)

In Part B, the treatment period will be extended until 50 ED have been accumulated. The duration of Part B will vary and is dependent upon the frequency of prophylactic infusion and the number of bleeding events. Blood sampling for inhibitor testing is required every 3-5 ED up to 20 ED, and again at 50 ED. As most subjects will begin prophylaxis 1x week, study visits during the first 20 ED are expected to occur monthly. However, it is understood that bleeding events resulting in added doses, delayed start of prophylaxis after first bleeds, or missed infusions due to difficult i.v. access may result in some variation in the number of ED a subject has obtained at each visit or the exact interval between visits. Likewise, those subjects who receive more frequent infusions may require study visits more often than once a month. (as of Amd 1)

After completing Part A or B, all (as of Amd 1) subjects will be offered continued treatment in an extension study until a total number of at least 100 ED per subject are accumulated. Participation will require (as of Amd 1) additional visits every 6 months.

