7.1.2.7 Interim visit – Only for Part B (30-40 ED) (as of Amd 1)

Visit only required for PUPs and MTPs who have less than 40 ED, 6 months after the Baseline visit. The intent is to have at least one scheduled visit between completion of 20 ED and the expected date of accumulating 50 ED. The primary purpose of the visit is to assess the well-being of the subject, ensure continued compliance with the treatment, and make any needed adjustments in dosage or infusion frequency based upon weight or bleeding events.

The following procedures and assessments will be performed:

- *Measurement of body height/length and weight*
- *Documentation of interval history including AEs and concomitant medication and Healthcare Resources Utilization Questionnaire (Appendix 14.2).*
- *Measurement of vital signs: Systolic and diastolic blood pressure, heart rate, and body temperature. (Blood pressure may be deferred if appropriate cuff size or equipment is not available).*
- *Check of EPD entries of interval treatment and bleeding history.*

Regular weekly contacts between parents and the site to check the EPD documentation until next clinic visit. (as of Amd 1)

7.1.2.8 Final Visit (end of the main study and start of the optional extension study)

For subjects in Part A (as of Amd 1), this visit will take place 6 months after baseline and at least 50 ED were accumulated, or in case of early termination.

For PUPs and MTPs in Part B, this visit will take place after 50 ED with study medication are accumulated, or in the case of early termination (as of Amd 6). It is expected 50 ED will be achieved for most subjects between 6 and 12 months after start of prophylactic treatment. (as of Amd 1)

The following procedures and assessments will be performed:

- *Physical examination including measurement of body height/length (as of Amd 1) and weight*

- **Measurement of vital signs: Systolic and diastolic blood pressure, heart rate, and body temperature. (Blood pressure may be deferred if appropriate cuff size or equipment is not available). (as of Amd 1)**
- Documentation of interval history including AEs and concomitant medication and **Healthcare Resources Utilization Questionnaire (Appendix 14.3). (as of Amd 1)**
- **Blood samples for laboratory tests:**
 - **Complete blood count [CBC]**

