This SAP describes the objective, study design, analysis sets, all endpoints, and statistical analysis methods for the interim analysis of the part B of study 13400, where Previously Untreated Patients (PUPs) and Minimally Treated Patients (MTPS) where treated. Planned end was 50 exposure days (EDs), in case of inhibitor development the subjects should leave the study and get treatment in the extension part or outside of the study. Complete details of Tables, Listing and Figures (TLFs) specifications as well as dataset details and data handling

specifications will be provided in "TLF specifications" and "Analysis Datasets" documents which are an integral part of this SAP.

The analysis of the 6-month data for Previously Treated Patients (PTPs) in Part A is complete and reported in the clinical study report A51496. This SAP is applicable to completion of Part B. The extension study is ongoing.

The data upon completion of Part B will be analyzed later. The overall study will be closed after all subjects in Parts A and B have completed their respective extensions, in accordance with the protocol definition of 'end of study' (that is, last visit of the last subject [including subjects in the extension study]).

Further details can be found in the Clinical study protocol, which contains comprehensive information on the study drug.

2. Study Objectives

General objectives of this study are:

Primary objective

• To demonstrate the safety and efficacy of treatment with BAY 81-8973 for prophylaxis and breakthrough bleeds in children with severe hemophilia A

Secondary objectives

- To assess the safety and efficacy of BAY 81-8973 during surgeries
- To assess incremental recovery of BAY 81-8973
- To characterize pharmacokinetics in a subset of children

As during part B of this study, where PUPs and MTPs were treated up to 50 EDs (or development of inhibitor) only few recovery and pharmacokinetic data were collected, the last two secondary objectives will be analyzed in the final analyses of the study where more data are available.

3. Study Design

From the protocol:

This is a phase-III multicenter, open-label uncontrolled study to demonstrate safety and efficacy of treatment with BAY 81-8973 for prophylaxis, breakthrough bleeds, and surgeries in children with severe hemophilia A. The study will be conducted worldwide.

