4.2 Handling of Dropouts

In this study, all efforts must be taken to engage patients to comply with all study procedures and to continue to be followed until the end of the study.

A subject who discontinues study participation prematurely for any reason is defined as a "dropout" if the subject has received at least one dose of study drug. At the time of discontinuation, subjects should be requested to have a final visit to have performed the procedures and evaluations scheduled for the final study visit as described for last visit. Subjects who are withdrawn after the start of treatment will not be replaced.

A subject is regarded a "screening failure" if he terminates the study for any reason (e.g., failure to satisfy the selection criteria) prior to the time point used for the definition of "dropout".

In all cases, the reason for withdrawal must be recorded in the electronic case report form (eCRF) and in the subject's medical records.

The number of subjects who prematurely discontinue the study during the treatment phase or during the post-treatment observation phase for any reason, as well as the reasons for premature discontinuation of study, will be displayed.

Subjects who prematurely withdraw prophylaxis treatment due to inhibitor development will be considered premature discontinuations from Part B, even though they may continue with ITI treatment in the extension phase. For this reason a separate tabulation of the reason for premature termination will be given, where all reasons connected to ITI or inhibitors will be combined to "INHIBITOR MANAGEMENT". In addition subjects, who prematurely

discontinued part B without a clinical reason (inhibitor, AE) or withdrawal of informed consent or protocol violation, but just for logistical problems to match exactly the 50 EDs, will be counted as completers in this table.

Subjects can be withdrawn at their parent's request, or at the investigator's discretion due to, for example, development of inhibitory antibody or lack of compliance. The reasons for withdrawal will be listed. The annualized number of total bleeds will be calculated for these withdrawn subjects, and the time of the last procedure in a visit or the last infusion in the EPD will serve as the end time point used for calculation.

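### The Part B bleed-free percentage has no common observation window, so early exits can only hold it at or above what full follow-up would show

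*SAP*

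**What the plan says.** The bleed-free percentage closes a list of other variables under Additional Efficacy Analysis in section 6.2 of the Part B SAP (version 2.0): "as well as proportion of subjects with no bleed". Neither that section nor any other visible text gives it a period, a minimum stay or a censoring rule.

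The analysis set is fixed: "All efficacy variables will be summarized using the ITT analysis set". Section 5.1 defines that set as "All subjects of the SAF, who have infusion/bleeding data", so a child with a few weeks of diary data is included.

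Follow-up differs between children by design:

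- **Completers.** Protocol section 7.1.2.8 (Final Visit): "It is expected 50 ED will be achieved for most subjects between 6 and 12 months after start of prophylactic treatment".
- **Inhibitor cases.** Part B SAP, Introduction: "in case of inhibitor development the subjects should leave the study". Section 4.2 adds: "Subjects who prematurely withdraw prophylaxis treatment due to inhibitor development will be considered premature discontinuations from Part B".
- **Timing of exits.** The protocol's benefit-risk assessment (section 1) places the inhibitor risk in the first 20 ED. Section 7.1.2 gives the early pace: "As most subjects will begin prophylaxis 1x week, study visits during the first 20 ED are expected to occur monthly". At one infusion a week, 20 ED is about 20 weeks.

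For withdrawn children, section 4.2 sets an end point only for the rate: "The annualized number of total bleeds will be calculated for these withdrawn subjects". Kaplan-Meier curves are planned in section 6.4.3, but for inhibitor occurrence and not for first bleed.

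**The concern.** An annualised rate divides by time observed; a raw zero-bleed percentage does not. The less time a child is watched, the more likely he is to finish with no bleed on record. In Part B one main cause of a short stay is an inhibitor, which is the outcome the sponsor most wants to avoid. An unfavourable safety course can therefore push up a favourable-looking efficacy percentage.

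Readers readily pick up bleed-free percentages for prophylaxis. Without a time base, this one cannot be read as the chance of staying bleed-free over any stated interval. It is also hard to compare between PUPs and MTPs if their exit patterns differ.

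**Working it through.** The plan states no figure for this variable and section 9.1 of the Part B SAP reports no formal sample-size determination, so there is nothing to reproduce.

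**Direction, without assumptions.** Once a bleed is recorded, longer observation cannot remove it. Cutting a child's follow-up short therefore leaves his status unchanged or turns a bleeder into a non-bleeder. Summed over children, the crude percentage is at or above the full follow-up value.

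**Does any stated period equalise follow-up?** The periods in section 6.2.2 that would apply end at the child's own final visit, last prophylactic infusion or inhibitor-related date. None sets a common length.

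**Size, under a constant bleed rate.** P(no bleed by time t) = exp(−λt). With a share d leaving at time s and the rest followed to T:

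crude = (1 − d)·exp(−λT) + d·exp(−λs)

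T = 9 months (0.75 year) is the middle of the protocol's 6 to 12 months. The values of λ, d and s are assumptions; the documents give none of them.

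At λ = 3 per year and d = 40%:

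- Full follow-up: exp(−3 × 0.75) = 0.105.
- Exit at 2.5 months: exp(−3 × 2.5/12) = 0.535; crude = 0.6 × 0.105 + 0.4 × 0.535 = 0.277, or 28%.
- Exit at 20 weeks (0.383 year): exp(−3 × 0.383) = 0.317; crude = 0.6 × 0.105 + 0.4 × 0.317 = 0.190, or 19%.

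Other rates, exit at 2.5 months, 20% to 50% leaving:

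- λ = 1: 54% to 64%, against 47%.
- λ = 6: 7% to 15%, against 1%.

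**Sensitivity, λ = 2 and exit at 10 weeks.** Full follow-up gives 22.3%. The crude figure is 26.9%, 33.8% or 45.2% with 10%, 25% or 50% leaving. If the 50% who leave bleed at twice the rate, the crude figure is 34.4%, against 13.6% for the same children followed in full.

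**Completers alone, λ = 2.** exp(−1) = 36.8% at 6 months and exp(−2) = 13.5% at 12 months. The figure lacks a fixed meaning even without drop-out.

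**Does Kaplan-Meier repair it?** In 4,000 simulated trials of 50 children (λ = 2, half leaving at 10 weeks), the mean Kaplan-Meier estimate at 9 months was 22.3%, against a true 22.3% and a crude 45.2%. The simulation made exit independent of bleeding.

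**The case against.** Several points on the other side are sound.

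- **Leaving early is not the same as being counted bleed-free.** A reader might infer that every early leaver is scored a success. He is scored so only if no bleed was recorded before exit; in the 2.5-month illustration, 1 − 0.535 = 46.5% of leavers have already bled. A child whose first dose treats a bleed may also fail to qualify, depending on the window used.
- **The SAP is silent; it has not adopted a flawed rule.** It calls its TLF and dataset specifications part of the plan, and these are not among the documents reviewed. A rule that determines the estimate still belongs in the SAP text.
- **Partial safeguards exist.** Sections 4.1 and 6.2.2 display efficacy by inhibitor status, and section 6 allows sensitivity analyses in the PPS, which requires completion. These reduce the problem, but the total, PUP and MTP columns still mix short and long stays, the PPS analysis is optional, and completers vary in duration. Some low-titre children may also remain in Part B.
- **The variable is minor.** It is absent from the secondary endpoints in the SAP Supplement (section 2.1), and efficacy is exploratory. A reader might infer that a planned comparison with Part A is spoiled, but the Part A SAP's endpoint lists contain no bleed-free percentage.
- **Kaplan-Meier is not free of bias.** The Part B SAP's background section links inhibitors with more bleeding complications, so censoring at inhibitor exit may be informative and the estimate still too favourable. That calls for a caveat. It does not justify the crude figure, which treats unobserved time as bleed-free.

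**Conclusion.** The point holds as a cheap improvement. The crude percentage in the total, PUP and MTP columns has no time base and can only equal or exceed what the same children would show with full follow-up. That direction needs no assumption. The size does: 28% or 19% against 10.5% rests on an assumed bleed rate, share leaving and exit time, and on equal bleed rates in leavers and completers.

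A reader might infer that the main Part B efficacy result is inflated. The documents do not support that. The primary variable is an annualised rate, section 4.2 carries it through for withdrawn children, and no success criterion is attached to the bleed-free percentage.

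**What to change.** In section 6.2 of the Part B SAP, report the Kaplan-Meier probability of remaining bleed-free at 6 months from the start of prophylaxis, censored at the end of the Part B prophylaxis period. Give the 95% CI and the number at risk, for total, PUPs and MTPs. State that censoring at inhibitor exit may be informative and that the estimate may still be favourable.

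If the crude percentage is kept, name its period and show follow-up time beside it. Do not restrict it to children observed for at least 6 months. Part B ends at 50 ED, so children who bleed or infuse more get there sooner; the restriction would drop them along with the inhibitor leavers.

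The cost is one extra table from infusion, bleed and visit dates already collected. The reported percentage will probably be lower where exits are early and frequent. It need not always be, because 6 months is shorter than many completers' stay: at 3 bleeds per year the 6-month value is exp(−1.5) = 22%, between the 19% and 28% crude figures above. Unlike them, it refers to a stated interval.
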